2.2 BACKGROUND

In a prior study,² we asked people on a 10-point scale how likely they were to have had COVID-19. About 20% of the sample reported 7 or higher on this 10-point scale, however only 4% of the sample tested positive. This suggests antibody testing has a large potential to correct beliefs about past infection and promote retesting for those who are antibody negative. However, a positive test could potentially reduce willingness to participate in repeat testing. Among those who tested positive, about 23% of the sample reported a 1 or 2 on a 10-point scale on how likely they were to have had COVID-19. These people may be less likely to retest for studies trying to depict the immune response over time. Underserved populations face different barriers to testing and these may vary within different communities and households. The diversity in Los Angeles allows us to assess how barriers to antibody testing differ for vulnerable groups. Data from our prior study show that Blacks and Latinos were 27 percentage points and 14 percentage points less likely to participate in testing compared to their white counterparts.² We also find that those with household income less than \$50,000 were 17 percentage points less likely to take-up antibody testing compared to those with household income greater than \$100,000. It is important to understand why these disparities exist. The proposed research will shed light on this issue by evaluating barriers/facilitators of testing including

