7.1 DISCONTINUATION OF STUDY INTERVENTION/EXPERIMENTAL MANIPULATION

Participants who decline testing initially will be offered an exit survey which will ask them for reasons for declining. We will longitudinally follow the initial cohort that completed baseline survey (including people who declined testing in wave 1) and offer an additional wave of testing 6 months after the first wave.

Participants can choose to withdraw from the study at any time, and this will be documented in their REDCap record. When a subject discontinues Wave 2 retesting but not from the study, remaining study procedures (data analysis) will be completed as indicated by the study protocol.

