9.2 SAMPLE SIZE DETERMINATION

We will recruit a cohort of 2,160 people (540 families), and stratify into 3 subgroups based on predictors of commitment to participation in testing programs. Randomization will be clustered by family. Sub-group membership will be based on the mean household survey response to the survey component. For the purposes of power analyses, we assume high Intra Cluster Correlation within family on uptake of repeat testing (>0.90).

Stratified Allocation Plan and Power Analysis (540 households, 2160 individuals)		
	Control	Intervention
Stratification	# households	# households
HTE Subgroup 1	60	60
HTE Subgroup 2	60	60

HTE Subgroup 3	60	60
% Seropositive in Baseline Test	10%	10%
Total Households Per Arm	180	180
Projected Average Treatment Effect Size	Reference Group	Reference+10%
Minimum Detectable Effect Size Compared to Controls (H4r)	±3%	
Detectable 3-subgroup HTE and Seropositivity (H1r, H2r, H3r)	±7%	

Assuming a similar effect size to prior studies in similar populations, we expect a 10 percentage point difference in repeat testing adherence between intervention and control groups. With 540 households, we are powered to detect as little as 3 percentage point difference between interventions and controls in the 540 households we will enroll. To assess heterogeneity of treatment effects (THE), there is more than 80% power to detect a between-subgroup difference of 7 percentage points, assuming 180 households in each sub-group.

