9.4 STATISTICAL ANALYSES

9.4.1 GENERAL APPROACH

Aim 1 (Hypotheses 1-5): Data from the baseline survey combined with data on which heads of households attended Time 1 testing will be used to address Aim 1. In particular, we will estimate logistic regressions where the dependent variable will be the binary indicator whether the head of household attended Time 1 testing (yes vs. no). The key independent variables will include: 1) prior COVID-19 testing, 2) which SARS-CoV-2 information sources are most trusted, 3) risk aversion, 4) heads of households or family member diagnosis of a health condition (e.g., diabetes, hypertension) and, 5) race/ethnicity, income, discriminatory incidences, household receipt of Supplemental Nutrition Assistance Program (SNAP) or Supplemental Security Income (SSI) benefits, and citing money as the biggest vaccine barrier.

$$\pi = \beta_0 + \beta_1 x_i + \varepsilon_i \quad [1]$$

$\pi = \ln\left(\frac{p}{1-p_i}\right)$; p_i , is the probability of attending Time 1 testing, by head of household i , and β_1 is each head of household reported social determinant of health. This will allow us to identify significant social and behavioral determinants for heterogeneity of effects (currently hypothesized in Hypotheses 1-5 above).

Aim 2 (Hypotheses 1r-4r): Aim 2 will involve regressing Time 2 retesting (yes vs. no) on the following items for Hypotheses 1r-4r: 1r) risk aversion, essential worker status, access to personal protective equipment, and risky forms of transportation (e.g., personal vehicle, carpool, bus), 2r) income, discriminatory incidences, employment status, whether heads of households personally, or other family members suffer from depression and/or mental health issues, and household receipt of Supplemental Nutrition Assistance Program (SNAP) or Supplemental Security Income (SSI) benefits, 3r) Time 1 seropositivity status and, 4r) the Financial Incentive and Messaging study arms.

$$\pi = \beta_0 + \beta_1 x_i + \beta_2 x_i + \beta_3 x_i + \varepsilon_i \quad [2]$$

For Hypotheses 1r-2r, $\pi = \ln\left(\frac{p}{1-p_i}\right)$, is the probability of Time 2 attendance by head of household i given they attended Time 1 testing; β_1 is the main effect of the head of household reported characteristic, β_2 is the main effect of the Financial Incentive, where the lottery condition is the reference, and β_3 is the interaction between the head of household reported social determinant of health and Financial Incentive.

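### The 7-point, more-than-80%-power claim for H1r/H2r does not hold for the Model 2 interaction among Time 1 attenders: power is about 10–27% even if all 540 households are analysed

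*Combined protocol and SAP*

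**What the plan says.** Section 9.2 sets the size: "We will recruit a cohort of 2,160 people (540 families), and stratify into 3 subgroups". For clustering, "we assume high Intra Cluster Correlation within family on uptake of repeat testing (>0.90". For the overall comparison, "we expect a 10 percentage point difference in repeat testing adherence between intervention and control groups". For heterogeneity of effect it says "there is more than 80% power to detect a between-subgroup difference of 7 percentage points, assuming 180 households in each sub-group". The row of the power table that carries the 7 points reads "Detectable 3-subgroup HTE and Seropositivity (H1r, H2r, H3r", so the figure is offered for the two heterogeneity hypotheses as well as for serostatus.

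Section 9.4.1 gives the analysis for H1r and H2r. In Model 2 the outcome "is the probability of Time 2 attendance by head of household i given they attended Time 1 testing". The term that tests heterogeneity is the product of the head's characteristic and the Financial Incentive, with the lottery condition as reference.

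On who is followed, section 7.1 says "We will longitudinally follow the initial cohort that completed baseline survey (including people who declined testing in wave 1", with a second wave of testing offered to this cohort. Aim 1 (Model 1) takes the head's attendance at Time 1 as a yes/no outcome, and Models 4a and 4b use Time 1 attendance as the reference time. No section gives a Time 1 attendance rate, a reference retest rate, an alpha level or its sidedness.

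**The concern.** The claim and the analysis differ in two ways. First, the claim is worded as a difference between sub-groups of 180 households, whereas Model 2 tests a difference between incentive effects. Such a contrast splits each sub-group by incentive arm and adds the variances of four cells. Second, the claim uses every enrolled household, whereas Model 2 keeps only heads who came to the first test.

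Which families respond to insurance and which to a lottery is a stated purpose of the trial. If the interaction terms are null, a reader of section 9.2 would conclude that differences of 7 points or more had been largely ruled out. If the true sensitivity is several times coarser, that conclusion would be wrong.

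**Working it through.** **Inputs from section 9.2:** 180 households per sub-group; 2,160/540 = 4 people per household; ICC 0.90 (the lower bound of what is assumed); average effect 10 points. The allocation table as extracted shows 60 + 60 households per sub-group, but a column may have been lost, so the 180 in the text is used.

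**Assumed, because not stated:** two-sided alpha 0.05; equal split on incentive, so 180/2 = 90 households per cell; the same reference (lottery-arm) retest rate p in both sub-groups, scanned over 2–80%; Time 1 attendance a. A normal approximation on the probability scale is used because 9.2 speaks in points, although Model 2 itself works in log-odds.

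**Step 1: the plan's own figure.** Take 7 points as a simple difference between two sub-groups of n = 180. Power = Φ{(0.07 − 1.96·√[2p̄(1−p̄)/n]) / √[p₁(1−p₁)/n + p₂(1−p₂)/n]}. For 50% v 57%: (0.07 − 1.96 × 0.0526)/0.0524 = −0.63, so power is 26%.

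| Comparison | 180 households | 720 people, clustering ignored |
|---|---|---|
| 10% v 17% | 49% | 97% |
| 30% v 37% | 29% | 80% |
| 50% v 57% | 26% | 76% |
| 70% v 77% | 32% | 85% |

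At household level, 80% is passed only near the extremes (2% v 9%: 83%; 92% v 99%: 90%). The nearest match to the claim at middling rates is the last column, which ignores the plan's own ICC. With it, the design effect is 1 + 3 × 0.90 = 3.7, and 720/3.7 = 194.6 effective people, giving 28% at 50% v 57%. The claim is therefore not reproduced at household level over 10–77%.

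**Step 2: the Model 2 contrast, full attendance.** Place the two sub-group effects 7 points apart around 10, i.e. 6.5 and 13.5 points. SE = √[Σ pₖ(1−pₖ)/90] over four cells. Power = Φ(0.07/SE − 1.96) + Φ(−0.07/SE − 1.96).

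- p = 50%: cells 0.50, 0.565, 0.50, 0.635; SE = √(0.97755/90) = 0.1042; 0.07/SE = 0.67; power 10%.
- p = 2%: cells 0.02, 0.085, 0.02, 0.155; SE = √(0.24795/90) = 0.0525; 0.07/SE = 1.33; power 27%.
- p = 80%: cells 0.80, 0.865, 0.80, 0.935; SE = √(0.49755/90) = 0.0744; 0.07/SE = 0.94; power 16%.

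The range is about 10–27%. Placing the effects at 10 and 17 points gives 10–23%. Placing them at 10 and 3 raises the top end, at p = 2%, to 33% (SE = √(0.1923/90) = 0.0462).

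**Step 3: detectable interaction at 80% power, p = 50%.** With cell rates 0.50 and 0.60 in both sub-groups, Σ p(1−p) = 2 × 0.25 + 2 × 0.24 = 0.98. Detectable difference = 2.8016 × √(0.98/n per cell), where 2.8016 = 1.96 + 0.8416. The power column repeats the p = 50% line of step 2 with 90·a per cell.

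| Attendance a | Heads per cell (90·a) | Detectable interaction | Power at 7 points |
|---|---|---|---|
| 100% | 90 | 29 points | 10% |
| 83% | 74.7 | 32 points | 9% |
| 70% | 63 | 35 points | 9% |
| 50% | 45 | 41 points | 8% |

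**Step 4: a more favourable reading.** If the characteristic is binary and splits all 540 heads evenly, each cell has 540/4 = 135. At p = 50% and full attendance the detectable interaction is 2.8016 × √(0.98/135) = 24 points, and power at 7 points is 13%.

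**The case against.** The strongest reply is that the 540 may already be tested families. Section 2.1 describes 540 family clusters that will be repeatedly tested. Section 10.1.1.2 places informed consent at the first test, and the schedule in 1.3 puts consent with enrolment and randomisation. The power table has a row for baseline seropositivity, and 9.1 frames the retest hypotheses relative to people who took a first test. On that reading attendance is close to 1 and most of the loss at Time 1 disappears. Section 7.1, Model 1 and Models 4a/4b point the other way, since all need non-attenders in the followed cohort. The documents do not settle it. The reply answers only the second mismatch, however: the figure already fails at 100% attendance.

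Several stronger readings are tempting and not supported:

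- *That conditioning on Time 1 is what breaks the claim.* It only worsens a figure that fails with all 180 households.
- *That analysing one head per household costs further power.* Section 9.2 counts households, and one head per household is one unit per household.
- *That attendance is capped by the prior study, where* "Blacks and Latinos were 27 percentage points and 14 percentage points less likely to participate in testing compared to their white counterparts". Those gaps come from another sample. Section 5 draws 1,000 households and section 6.3 lists 6,222 names to reach 540, so refusals may be absorbed before enrolment.
- *That the loss must fall mainly on the least committed sub-group.* This is plausible, but no rate by sub-group is given. Section 9.4.5 also lets demographics seen after a week of testing set the stratification thresholds, so the sub-groups cannot be taken as fixed before testing.
- *That the 7 points can be scaled by attendance.* At 83% this gives 7/√0.83 = 7.7 points against 32 in step 3, about four times too favourable, because it starts from an unsupported figure.

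**Conclusion.** The concern holds. The stated power for H1r/H2r is not delivered by the analysis planned for them. For a 7-point sub-group by incentive interaction it is about 10–27% with every household analysed, against the more than 80% stated. At a 50% reference rate the detectable interaction is about 29 points, rising to 32–41 points for attendance between 83% and 50%.

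The exact values rest on two-sided alpha 0.05, equal cells, a 10-point average effect and the assumed reference and attendance rates. The conclusion does not depend on a particular choice among them: no reference rate scanned for the interaction at household level, and neither alternative placement of the effects, comes near 80%. The size of the Time 1 loss itself cannot be fixed from the documents. A reader might infer from the shared table row that H3r fails in the same way. That does not follow, because H3r uses a different model on individuals (Model 3), and nothing is concluded about it here.

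**What to change.** In section 9.2:

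1. Withdraw the 7-point, more-than-80% claim for H1r/H2r, in the sentence and in the table row.
2. Restate the detectable difference for the Model 2 interaction among heads who attend Time 1, giving the alpha and sidedness, the reference retest rate and the assumed Time 1 attendance. It should be computed for that interaction and not obtained by rescaling the 7 points.
3. Say whether 540, and 180 per sub-group, means surveyed and randomised households or tested households.
4. If Model 2 is instead run on all randomised heads, with non-attendance at Time 1 counted as no retest, say so in 9.4.1 and give the figure for that set.

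The cost is a recalculation and the rewording of one sentence and one table row. No participants or data are added. The stated sensitivity becomes less favourable, and a null interaction can then be read for what it is.

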9.3 POPULATIONS FOR ANALYSES

Sampling low-income populations is important for research on disparities, however, recruiting this population is challenging because they often lack consistent contact information, do not have internet access, and mistrust research. We will use a novel way of recruiting this population by partnering with AltaMed Health Services, the largest FQHC in the United States that serves overwhelmingly a low-income and minority population Partnering with an FQHC will build trust and also provide us access to reliable contact information.

9.4 STATISTICAL ANALYSES

9.4.1 GENERAL APPROACH

Aim 1 (Hypotheses 1-5): Data from the baseline survey combined with data on which heads of households attended Time 1 testing will be used to address Aim 1. In particular, we will estimate logistic regressions where the dependent variable will be the binary indicator whether the head of household attended Time 1 testing (yes vs. no). The key independent variables will include: 1) prior COVID-19 testing, 2) which SARS-CoV-2 information sources are most trusted, 3) risk aversion, 4) heads of households or family member diagnosis of a health condition (e.g., diabetes, hypertension) and, 5) race/ethnicity, income, discriminatory incidences, household receipt of Supplemental Nutrition Assistance Program (SNAP) or Supplemental Security Income (SSI) benefits, and citing money as the biggest vaccine barrier.

$$\pi = \beta_0 + \beta_1 x_i + \varepsilon_i \quad [1]$$

$\pi = \ln\left(\frac{p}{1-p_i}\right)$; p_i , is the probability of attending Time 1 testing, by head of household i , and β_1 is each head of household reported social determinant of health. This will allow us to identify significant social and behavioral determinants for heterogeneity of effects (currently hypothesized in Hypotheses 1-5 above).

Aim 2 (Hypotheses 1r-4r): Aim 2 will involve regressing Time 2 retesting (yes vs. no) on the following items for Hypotheses 1r-4r: 1r) risk aversion, essential worker status, access to personal protective equipment, and risky forms of transportation (e.g., personal vehicle, carpool, bus), 2r) income, discriminatory incidences, employment status, whether heads of households personally, or other family members suffer from depression and/or mental health issues, and household receipt of Supplemental Nutrition Assistance Program (SNAP) or Supplemental Security Income (SSI) benefits, 3r) Time 1 seropositivity status and, 4r) the Financial Incentive and Messaging study arms.

$$\pi = \beta_0 + \beta_1 x_i + \beta_2 x_i + \beta_3 x_i + \varepsilon_i \quad [2]$$

For Hypotheses 1r-2r, $\pi = \ln\left(\frac{p}{1-p_i}\right)$, is the probability of Time 2 attendance by head of household i given they attended Time 1 testing; β_1 is the main effect of the head of household reported characteristic, β_2 is the main effect of the Financial Incentive, where the lottery condition is the reference, and β_3 is the interaction between the head of household reported social determinant of health and Financial Incentive.

$$\pi = \beta_0 + \beta_1 x_{ij} + \eta_j + \varepsilon_i \quad [3]$$

For Hypothesis 3r, we will use a simple mixed-effects logistic model, where $\pi = \ln\left(\frac{p}{1-p_i}\right)$, is the probability of Time 2 attendance by individual i in household j given they attended Time 1 testing; β_1 is seropositivity status at Time 1 (yes vs. no); and η_j is the random intercept for each household capturing household-level effects.

We will use two separate models for Hypothesis 4r.

$$\pi = \beta_0 + \beta_1 x_{ij} + \beta_2 x_{ij} + \beta_3 x_{ij} + \beta_4 x_{ij} + \beta_5 x_{ij} + \eta_j + \varepsilon_i \quad [4a]$$

Model 4a will assess the probability, $\pi = \ln\left(\frac{p}{1-p_i}\right)$, of testing attendance for individual i in household j , where β_1 is the main effect for testing time (reference = Time 1); β_2 is the main effect for Financial Incentives (reference = lottery condition); β_3 is the main effect for Messaging (reference = personal); β_4 is the interaction between testing time and Financial Incentives; β_5 is the interaction between testing time and Messaging; and η_j is the random intercept for each household.

$$\pi = \beta_0 + \beta_1 x_{ij} + \beta_2 x_{ij} + \beta_3 x_{ij} + \beta_4 x_{ij} + \beta_5 x_{ij} + \beta_6 x_{ij} + \beta_7 x_{ij} + \eta_j + \varepsilon_i \quad [4b]$$

Model 4b will assess the probability, $\pi = \ln\left(\frac{p}{1-p_i}\right)$, of testing attendance for individual i in household j , where β_1 is the main effect for testing time (reference = Time 1); β_2 through β_4 are the main effects for study arm (personal messaging and loss protection, family messaging and lottery, family messaging and loss protection), where personal messaging and lottery is the reference group; β_5 through β_7 are the interactions between study arm and testing time; and η_j is the random intercept for each household.

For Models 4a and 4b, we will use unrestricted random sampling to select 3,000 observations, 2,000 times, clustered by household to bootstrap 95% confidence intervals for probability differences. We

will test differences in effect sizes for Model 4a (β_4 vs. β_5) and 4b (β_5 vs. β_6 ; β_5 vs. β_7 ; β_6 vs. β_7) using equality of regression coefficients tests.⁶ We will also calculate the inverse of observed probabilities to derive the Number Needed to Intervene on (NNI), and calculate standard errors by taking the square root of $P * (1 - P)/N$.⁷

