5.5 STRATEGIES FOR RECRUITMENT AND RETENTION

Our study population will consist of patients on the registries of AltaMed's 12 Los Angeles County primary care clinics, and we will draw a simple random sample of 1000 patient households without replacement. Patients will be randomly selected by address and confirmed to be patients by medical identification number. All members of the household, both adults and children over the age of 5, are invited to participate in testing, but at least one parent and one child must participate in order for the household to qualify.

Potential study participants must meet the inclusion criteria prior to enrollment. We will use stratified random sampling within the AltaMed patient registry to identify AltaMed patients (and their family members) for study recruitment. Stratification will be by distance to the testing site: using zipcodes, we identified the median distance of patients empanelled in any Los Angeles County AltaMed clinic to the testing site, and we then identified roughly equal random samples of those living less than this median distance (n=3148) and those living more than this median distance (n=3074). In contacting individuals in this sample, all adults and children 5 years of age and older will be invited to participate in testing; at least one adult and one child from a household must be willing to participate in order to be eligible for testing.

Only one adult member (head of household) will be completing the survey. Minors will not be completing survey questions. Children under 5 years of age will be excluded from the study as Tasso SST devices are not recommended for children under 5.

Study participants will be recruited via phone by a culturally competent, bilingual research coordinator from The Henne Group. Consent for participating in the study will be a two-part process. As part of the initial recruitment call, The Henne Group callers will describe the study and ask adult (head of household) if they would like to participate in a survey about COVID-19 and social determinants of health. Consent to participate

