9.1 STATISTICAL HYPOTHESES

The figure below provides a conceptual diagram for thinking about what factors may influence testing take-up and retesting. Testing take-up would depend on several factors, including prior beliefs about infection, health literacy, information networks, health conditions, demographics and socio-economics. We have the following hypothesis based on analysis of literature on testing for HIV and Hepatitis as well as preliminary analysis of data from our prior study:

Hypothesis 1: Those who believe that they have been infected in the past would be more likely agree to testing to confirm that they have antibodies and potential immunity; **Hypothesis 2:** People with poor health literacy will be less likely to agree to testing as they might find it daunting to understand what the test does and how to interpret results; **Hypothesis 3:** Those who are risk averse would be more likely to agree to testing as it reduces uncertainty about serostatus; **Hypothesis 4:** Those with preexisting health conditions would be more likely to agree to testing as they face higher risks from COVID-19 and thus have more to gain from learning serostatus; **Hypothesis 5:** Minorities and those in lower socio-

economic strata would be less likely to agree to testing due to fear of discrimination, lack of trust in health care/research, poor past experience, and perception of being at low risk of infection. We also generate hypotheses for facilitators to retesting (r) relative to those who take a first test **Hypothesis 1r:** Persons who practice low COVID-19 mitigation, exhibit risk-seeking and have high exposure risk may respond to a lottery retest incentive. **Hypothesis 2r:** Those persons with low income, unemployed, or have high stress or anxiety may respond most to insurance of incentives. **Hypothesis 3r:** Persons who are sero+ at baseline will be less likely to return for a retest. **Hypothesis 4r:** Lottery insurance and family messaging will induce higher retesting rates. Hypotheses 1-5 are covariates that may affect agreeing to the test. Hypotheses 1r and 2r refer to heterogeneity of treatment effects for retesting, while 3r and 4r are main effects on retesting.

Conceptual diagram

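### Hypothesis 4 and the mental-health part of Hypothesis 2r concern a person's own condition, but each listed predictor also admits a family member's condition

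*Combined protocol and SAP*

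**What the plan says.** Section 9.1 states Hypothesis 4 as "Those with preexisting health conditions would be more likely to agree to testing as they face higher risks from COVID-19", adding that such people have more to gain from learning their serostatus. Hypothesis 2r reads "Those persons with low income, unemployed, or have high stress or anxiety may respond most to insurance of incentives". Both describe the person whose behaviour is being explained.

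Section 9.4.1 sets the Aim 1 outcome as "the binary indicator whether the head of household attended Time 1 testing (yes vs. no"). Model 2, used for Hypothesis 2r, takes the head's Time 2 attendance given Time 1 attendance. The predictor for Hypothesis 4 is "heads of households or family member diagnosis of a health condition (e.g., diabetes, hypertension"). The mental-health predictor for Hypothesis 2r is "whether heads of households personally, or other family members suffer from depression and/or mental health issues", one of several items listed for that hypothesis.

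Equation [1] has one predictor and one coefficient, described as "each head of household reported social determinant of health". Equation [2] has one characteristic, the Financial Incentive and their interaction. Section 5.5 says "Only one adult member (head of household) will be completing the survey", so anything known from the survey about relatives comes from the head. Section 9.4.2 carries significant determinants from Hypotheses 1 to 5 into the heterogeneity analysis.

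**The concern.** The hypotheses and the outcome are about the head; the predictors are about the head or someone else in the family. Read as one yes/no item, a healthy head whose spouse has hypertension counts as having a preexisting condition, and an untroubled head with a depressed relative counts as distressed. A positive answer also becomes more likely as the household grows, whatever the head's own health.

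Two different errors could follow. If only the head's own condition drives attendance, the exposed group is mixed with unaffected heads and the estimate shrinks. If only a relative's condition matters, the item still shows an effect, and Hypothesis 4 would be credited although own risk played no part. The second route is plausible in this trial: Section 4.1 bases the family message on concern for loved ones. A wrong reading could then pass through Section 9.4.2 into the choice of moderators.

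**Working it through.** **Reproducing the plan's figure.** There is none on this point. The 7-point, 80%-power statement in Section 9.2 concerns subgroup differences in general and does not depend on how these items are coded.

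**Step 1, text side by side.**

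| | Hypothesis 4 | Hypothesis 2r, mental-health item |
|---|---|---|
| Whose condition (9.1) | the person's own | the person's own |
| Whose attendance (9.4.1) | head, Time 1 | head, Time 2 given Time 1 |
| Whose condition in the predictor (9.4.1) | head or family member | head or other family members |
| Terms for the characteristic | one | one, plus its interaction with incentive |

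**Step 2, inputs for an illustration.** Section 9.2 says "We will recruit a cohort of 2,160 people (540 families"), so 2,160/540 = 4 enrolled people per family. Everything else is assumed: two adults and two children; adult prevalence q = 20-40%; child prevalence c = 2-5%; correlation r between the two adults' diagnoses = 0-0.3; children independent.

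**Step 3, formulas for a combined item.**
- P(any) = 1 − [(1−q)² + r·q(1−q)]·(1−c)²
- Share of flagged heads without the condition = 1 − q/P(any)
- If only the head's condition matters, the observed difference is the true difference × q/P(any), because every unflagged head is unaffected.
- If only a relative's condition matters, it is the true difference × [1 − (1−q)(1−c)²]/P(any).

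**Step 4, extremes of the grid for the first scenario.**
- q = 20%, c = 5%, r = 0: P(any) = 1 − 0.64 × 0.9025 = 0.422. Unaffected share = 1 − 0.20/0.422 = 53%. A 10-point own effect appears as 4.7 points.
- q = 40%, c = 2%, r = 0.3: P(any) = 1 − (0.36 + 0.072) × 0.9604 = 0.585. Unaffected share = 1 − 0.40/0.585 = 32%. A 10-point own effect appears as 6.8 points.

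**Step 5, extremes for the second scenario.** A 10-point relative-only effect appears as 0.2317/0.3853 × 10 = 6.0 points (q = 20%, c = 2%, r = 0) up to 0.4585/0.6101 × 10 = 7.5 points (q = 40%, c = 5%, r = 0.3).

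**Step 6, power, first scenario.** Assume 540 heads, 50% base attendance, a 10-point own effect and a two-sided 5% two-proportion test. An own-condition indicator gives 46% (q = 20%) to 63% (q = 40%). The combined item gives 19% to 35% over the grid. The number of surveyed heads in Model 1 is not stated, so 540 is also an assumption.

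**Step 7, sensitivity to household make-up.** With one adult and one child (q = 20-40%, c = 2-5%) the unaffected share is 3-17%. With one adult and three children it is 8-36%. In the other direction, if all four members had the same prevalence p of 10-20%, as might be tried for mental health, the affected share p/[1 − (1−p)⁴] is 29-34%, so 66-71% of flagged heads would be unaffected. Counting two adults only, p/[1 − (1−p)²] gives 53-56% affected.

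**The case against.** The strongest reply is that the coding is inferred. Section 9.4.1 names variables and gives no scoring rule, and the survey instrument is not in the documents. The wording also fits two answers entered as separate determinants, in which case nothing is diluted. This stands as a limit on the claim. It does not remove the point: each phrase is one listed entry joined by an or, the equations show one term, and if two items were intended the plan still does not say which one tests the hypothesis.

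Second, the documents supply no prevalence, adult/child split or family correlation of diagnoses, and Section 5.5 requires only one adult and one child. Four per family is the planned enrolled cohort, not the household size of all surveyed heads. This stands too, so the percentages can only illustrate.

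Third, a household-level exposure is defensible in a study of families. That is fair as a research question, but it is not the mechanism that Section 9.1 gives for Hypothesis 4.

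Fourth, the consequences are limited. Understanding determinants is a secondary objective in Sections 1.1 and 3, and Section 9.1 calls Hypotheses 1 to 5 covariates. This stands and sets the severity.

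**Conclusion.** The mismatch between hypothesis and predictor is in the text. On the natural reading, a result from either combined item cannot be reported as a test of Hypothesis 4 or of the mental-health part of Hypothesis 2r. Under the two-adult, two-child assumptions, about 32-53% of flagged heads would lack the condition and a 10-point own effect would show as about 4.7-6.8 points. One-adult households give much smaller dilution.

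A reader might infer four stronger things that the documents do not support:
- That the plan states an any-member scoring rule. It states none.
- That a particular share of exposed heads is misclassified. The share depends wholly on assumed prevalence and family make-up.
- That the tests are both diluted and wrongly credited. These are alternatives: full dilution needs a relative's condition to have no effect, misattribution needs it to have one.
- That Hypothesis 4 will be missed because of this item. That rests on an assumed effect and base rate, and even own-condition coding reaches only 46-63% power at 540 heads.

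Severity is low. Neither the exposure in Hypothesis 4 nor the moderator in Hypothesis 2r is randomised, only one of several Hypothesis 2r items is involved, and the randomised Hypothesis 4r comparison in Models 4a and 4b does not use these predictors.

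**What to change.** In Section 9.4.1, replace each either/or item with two indicators in the same model: the head's own diagnosis, and a diagnosis in another household member. Test Hypothesis 4 on the own term in Model 1. Test the mental-health part of Hypothesis 2r on the interaction of the own term with Financial Incentive in Model 2. Report the family-member term separately, as a family-concern effect.

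If the survey holds only a combined answer, label the result as a condition in the household and do not report it as a test of either hypothesis. Do not fill the gap with AltaMed record diagnoses. Sections 5.5, 10.1.1 and 10.1.1.1 describe signed consent and HIPAA authorisation only at the test appointment, so heads who do not attend would lack them and missingness would follow the Model 1 outcome.

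The cost is one extra coefficient per model, plus its interaction in Model 2, with some loss of precision where own and family diagnoses are correlated. If the survey question is combined and can still be changed, it needs a small split. Design, randomisation and sample size do not change.
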